6.3.8 Medical care upon termination of the clinical investigation

The study participants will not receive any study-specific treatment after the final visit. Any further treatment, if needed, will be proposed to the subject by the investigator at their discretion.

6.3.9 Screening/baseline failures

Data for screening/baseline failures (eligible subjects who did not receive investigational device for whatever reason) will be collected in source documentation at the site and documented in the Screening log but will not be entered into the CRF.

6.3.10 Subject confidentiality

This CIP, other study documentation, data, and all other information generated will be held in strict confidence. No information concerning the clinical investigation or the data will be released to any unauthorized third party without prior written approval of the Sponsor.

Personal subject data will be kept confidential in compliance with the European Data Protection Directive and other applicable international and national requirements.

The investigator must ensure that anonymity of the study participants will be maintained and that their identities are protected from unauthorized parties. On the CRF or any other documents submitted to the Sponsor or Sponsor's representative, subjects must be identified only by their identification codes; use of names, initials, addresses, telephone numbers, electronic addresses or similar information is prohibited. The investigator will keep the original of the Subject Identification Log (including complete name and date of birth of each subject) in his/her file. The investigator must maintain these documents in strict confidence.

To allow compliance with good clinical practice (GCP), all subjects will be asked for consent regarding the access to their personal clinical study-related data for monitoring, audits, and inspections as well as regarding transmission and storage of their anonymous data for the duration defined in the current GCP regulation; a respective statement will be part of the Informed consent form (ICF). Professionals with access to source data for monitoring, audits and inspections are bound to preserve strict confidentiality.

6.4 Assessments and procedures

Assessments and procedures that will be performed during the investigation are described below. The exact timing of each assessment is indicated in Table 1. Schedule of procedures and events and in section 6.1.4.

It is the investigator's obligation to assure documentation of all relevant data in the subject's medical record, such as medical history and concomitant diseases, date of enrolment into the clinical investigation, visit dates, results of examinations, application of medical device, and AEs.

6.4.1 Demographic data

The following demographic data will be collected: date of birth, gender and race.

6.4.2 Medical history

Medical history will be collected at Day 0, from subject interview and medical records (if available), covering relevant past medical history with particular reference to facial aestetic or surgical procedures.

6.4.3 Pregnancy test

In females of childbearing potential, including women who are postmenopausal for less than 12 months, a urine pregnancy test will be performed using a dipstick test with sensitivity of \leq 20 mLU of human chorionic gonadotropin per mL. The result will be recorded in the subject's medical record and the CRF.

6.4.4 Photography

Photographs of the subjects are taken as part of routine practice at the clinical site before the application of the medical device at the Baseline visit and after the intervention.

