6.1.2 Secondary performance endpoints

- The average change versus baseline in the NLF-SRS grade at Week 4 and Week 36 as evaluated by the investigator.
- The proportion of subjects with the NLF-SRS grade reduced by ≥1 point versus baseline at Week 4 and Week 36
- The proportion of subjects with aesthetic improvement at Week 4, Week 24 and Week 36, as evaluated by the investigator using the Global Aesthetic Improvement Scale (GAIS)
- Subjects' satisfaction with aesthetic outcome of the treatment at Week 4, Week 24 and Week 36, as evaluated by the subject
- The average pain intensity during and after the treatment, as evaluated by the subject using an 11-point Numeric Pain Rating Scale (NPRS) immediately after the last injection and 15 min. thereafter, respectively.
- The proportion of subjects with the NLF-SRS grade reduced by ≥1 point versus baseline at Week 24 as evaluated by the independent reviewer of photographs.

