6.4.6 Aesthetic improvement/GAIS assessment

The aesthetic improvement after correction of nasolabial folds will be evaluated at Week 4, 24 and 36 by the investigator using the Global Aesthetic Improvement Scale (GAIS)¹⁹, presented in **Table 5**, and recorded in the CRF.

Table 5. Global Aesthetic Improvement Scale (GAIS)

Category	Description
Very much improved	Optimal aesthetic result for the implant in this patient.
Much improved	Marked improvement in appearance from the initial condition, but not completely optimal for this patient. A Touch-up would slightly improve the result.
Improved	Obvious improvement in appearance from the initial condition, but a Touch-up or retreatment is indicated.
No change	The appearance is essentially the same as the original condition.
Worse	The appearance is worse than the original condition.

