6.4.9 Outcome evaluation by the independent reviewer of photographs

An independent reviewer will evaluate the treatment outcome using the NLF-SRS scale and based on the photographs. Photographic reviewer, who will assess treatment effect based on photographs of the subjects, will be dislocated from the investigation sites and will not discuss any findings with the investigators or independent clinical evaluators during the trial and until the final database lock. Moreover, an evaluation of nasolabial folds severity by an independent blinded photographic reviewer using the 5-point NLF-SRS scale and based on photographs will take place at the end of the study.

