2.4 Additional Endpoints

- The proportion of subjects with the NLF-SRS grade reduced by ≥2 points versus baseline at Week 4, 24 and Week 36.
- The proportion of subjects with the NLF-SRS grade reduced by ≥1 point versus baseline at Weeks 4 and 36 as evaluated by the independent reviewer of photographs.

3 Statistical Analysis Sets

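### Photographs for the blinded reviewer's responder endpoints follow site routine, with no visible standardisation, so image conditions can change who counts as a responder

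*Protocol*

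**What the plan says.** Protocol 6.4.4 is a single sentence. It states that "Photographs of the subjects are taken as part of routine practice at the clinical site", before the device is applied at Baseline and again after the intervention. Table 1 and section 6.1.4 fix when photographs are taken: Baseline, Weeks 4, 24 and 36, and optionally Week 2. They do not say how.

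Section 6.4.9 gives these photographs a measuring role. It provides for "an evaluation of nasolabial folds severity by an independent blinded photographic reviewer using the 5-point NLF-SRS scale and based on photographs" at the end of the study, with a reviewer located away from the sites.

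The resulting grades feed three responder endpoints:
- Protocol 6.1.2 and SAP 2.2 list as secondary the proportion reduced by at least 1 point "versus baseline at Week 24 as evaluated by the independent reviewer of photographs".
- SAP 2.4 adds the same proportion "at Weeks 4 and 36 as evaluated by the independent reviewer of photographs".

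Under SAP sections 4, 4.3.2 and 4.4, the grade analysed is the mean of the left and right folds, and a responder has a fall of at least 1 in that mean.

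No visible text in either document covers view, camera distance, lighting, facial expression or make-up removal for photography. The only make-up rule (6.2.2 and 6.3.7) covers the 12 hours after injection. On the photo grades, SAP 4.7 deals only with file format and delivery time.

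**The concern.** For the independent reviewer the photograph is the measuring instrument. The NLF-SRS in Protocol 6.4.5 grades visible fold depth, and light direction, head angle, expression and make-up can all alter apparent depth. If they differ between a subject's baseline and follow-up images, the difference enters the change score. Blinding does not remove it, because it lies in the material being graded.

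The trial has one open-label arm, and the investigator who treats also grades the primary endpoints. The photo review is the only independent reading to which the documents assign an assessment (6.4.9 also mentions independent clinical evaluators but gives them no task). Random differences in image conditions would blur that reading. Differences that follow the visit, such as softer light at follow-up, would bias it.

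**Working it through.** **The plan's own figure.** Protocol 7.1 (n = 60) and SAP section 1 (n = 40 to 60) give the half-width of a two-sided 95% normal-approximation interval for a proportion of 0.900.
- n = 60: 1.96 × √(0.9 × 0.1 / 60) = 0.0759, stated as 0.076.
- n = 40: 1.96 × √(0.9 × 0.1 / 40) = 0.0930, stated as 0.093.

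Both reproduce. They serve below only as a yardstick; the SAP summarises the photo endpoints in frequency tables.

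**How little it takes to change status.**
- True falls of 1 and 1: mean 1.0, responder. One fold misread by one grade: mean 0.5, non-responder.
- True falls of 1 and 0: mean 0.5, non-responder. One fold misread by one grade: mean 1.0, responder.

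**Illustration.** The documents give no error rate, so q is an assumption. The true rate is set to the plan's 0.900, and the other 10% of subjects do not change. A shift is one grade, up or down equally often. Three models:

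- **A.** The shift hits both folds and occurs independently in the baseline and the follow-up photo set, each with probability q. A one-grade responder is lost, and a non-changer gained, with probability (q/2)(1 − q/2) + (1 − q)(q/2). At q = 10% this is 0.0475 + 0.0450 = 0.0925; at q = 20% it is 0.09 + 0.08 = 0.17. A two-grade responder is lost with probability (q/2)² = 0.0025 or 0.01.
- **B.** The shift acts once, on the change score, on both folds together. A one-grade responder is lost, and a non-changer gained, with probability q/2 = 0.05 or 0.10. A two-grade responder is never lost.
- **C.** The shift acts once on each fold's change score, independently between folds. A one-grade responder is lost with probability 2(q/2)(1 − q) + (q/2)² = 0.0925 or 0.17. A non-changer is gained with probability (q/2)² = 0.0025 or 0.01. A two-grade responder is never lost.

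Observed rate = Σ (share of subjects) × (probability of being read as a responder). Examples for model A at q = 10%:
- All responders fall one grade: 0.9 × 0.9075 + 0.1 × 0.0925 = 0.826.
- Half fall two grades: 0.45 × 0.9075 + 0.45 × 0.9975 + 0.1 × 0.0925 = 0.8665.

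| Model | Responders' true fall | q = 10% | q = 20% |
|---|---|---|---|
| A | all one grade | 82.6% | 76.4% |
| A | half one, half two | 86.7% | 83.6% |
| B | all one grade | 86.0% | 82.0% |
| B | half one, half two | 88.3% | 86.5% |
| C | all one grade | 81.7% | 74.8% |
| C | half one, half two | 85.9% | 82.5% |

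Starting from model A with one-grade falls and changing one assumption at a time (first three rows) gives about 83 to 87% and 76 to 84%. All six rows span about 82 to 88% and 75 to 87%. The 7.4-point loss in the first row at q = 10% is about the size of the 7.6-point half-width at n = 60, and a sampling interval would not reflect it.

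**Systematic shift.** Suppose follow-up images make both folds look one grade different in 10% of subjects, always in the same direction, and all responders fall by one grade. If folds look shallower: 0.9 + 0.1 × 0.10 = 0.91. If folds look deeper: 0.9 × (1 − 0.10) = 0.81.

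**The case against.** The strongest reply is that the stake is limited. The affected endpoints are secondary or additional, the study is descriptive with no hypothesis test, and the reviewer is blinded and off-site. Photo visits have fixed windows. All of that stands and bounds the importance of the point.

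The error model can also be challenged. No value of q comes from the documents. The lowest figures need every responder to fall by exactly one grade, whereas the SAP's endpoint for falls of 2 or more contemplates larger ones. Model A applies q to two photo sets, so q = 10% alters 2 × 0.0925 = 18.5% of change scores. For these reasons only ranges are given.

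A reader might infer that having three or more sites with different routines is itself the problem. The documents do not support that: the endpoint is a within-subject change, so if a subject stays at one site, stable differences between sites largely cancel. What matters is drift between a subject's own visits. The documents do not say that practice drifts; they leave it uncontrolled.

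More instructions might exist elsewhere. The contents list places 6.4.4 and 6.4.5 on different pages although the visible text is short, and a site photo manual is possible. But the sentence in 6.4.4 is complete, carries no redaction mark and names routine practice as the method, and no manual is cited. The page gap does not show that text was removed.

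**Conclusion.** The point holds for the photo-based endpoints. Routine practice is the stated method for images that alone determine a secondary and two additional responder endpoints, and no visible rule keeps a subject's baseline and follow-up images comparable. Image conditions can decide responder status; the documents do not show that they will.

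For an assumed true rate of 90%, a 10% chance of a one-grade shift gives roughly 83 to 87% observed, and a 20% chance roughly 76 to 84%. The ranges widen to 82 to 88% and 75 to 87% when assumptions are combined or folds are misread separately. These figures rest on assumed error rates, symmetric shifts and the assumed mix of one- and two-grade falls. A shift tied to the follow-up visit could move the rate up or down.

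Three stronger readings are not supported:
- That the primary result is compromised. The primary endpoints use the investigator's own grading under 6.4.5, not the photographs.
- That disagreement between reviewer and investigator would carry no information. Noisy grades still inform, only less.
- That GAIS is affected too. Section 6.4.6 has the investigator grade it and does not base it on the photographs; how the investigator recalls the initial condition is a separate question, with no effect shown here.

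**What to change.** In Protocol 6.4.4, replace the reliance on routine practice with a short standard photo instruction for Baseline, Week 4, Week 24 and Week 36:
- the same frontal and left and right oblique views;
- the same camera distance and lighting set-up within each site;
- a relaxed, neutral expression and no make-up;
- follow-up framing matched to the subject's baseline image;
- a retake at the same visit if these conditions are not met.

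Photographs are already scheduled at these visits, so no visit or reader is added. The cost is a few extra minutes per visit, brief site instruction, a stable set-up at each site and someone to judge whether a retake is needed. The instruction must be in place before the first subject is treated, because a baseline image cannot be retaken afterwards.

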6.4.5 NLF-SRS grading of nasolabial folds

NLF-SRS is a validated, 5-point rating scale ranging from Grade 0 (none) to Grade 4 (extreme) as outlined in

Table **3**3 and 4. The severity of nasolabial folds will be evaluated by the investigator according to the NLF-SRS. The left and right nasolabial fold will be separately graded, and the assigned grades will be recorded in the subject's record and the CRF.

 Table 3. Nasolabial Folds Severity Rating Scale (NLF-SRS)

 Table 4 CROMA - NLF Severity Rating Scale (NLF-SRS)

CROMA NLF-	Description
------------	-------------

SRS grade	
0	None/minimal: No visible/minimal nasolabial folds
1	Mild: Shallow but visible nasolabial fold with a slight indentation
2	Moderate: Moderately deep nasolabial fold
3	Severe: Very deep nasolabial fold with prominent facial feature
4	Extreme: Extremely deep and long nasolabial fold with skin redundancy

6.4.6 Aesthetic improvement/GAIS assessment

The aesthetic improvement after correction of nasolabial folds will be evaluated at Week 4, 24 and 36 by the investigator using the Global Aesthetic Improvement Scale (GAIS)¹⁹, presented in **Table 5**, and recorded in the CRF.

Table 5. Global Aesthetic Improvement Scale (GAIS)

Category	Description
Very much improved	Optimal aesthetic result for the implant in this patient.
Much improved	Marked improvement in appearance from the initial condition, but not completely optimal for this patient. A Touch-up would slightly improve the result.
Improved	Obvious improvement in appearance from the initial condition, but a Touch-up or retreatment is indicated.
No change	The appearance is essentially the same as the original condition.
Worse	The appearance is worse than the original condition.

6.4.7 Pain assessment

After initial administration and optional Touch-up treatment of the investigational device, the subject will be asked by the investigator to quantify the pain associated with the procedure by means of a semi-quantitative 11-point Numeric Pain Rating Scale (NPRS), where 0 corresponds to no pain, and 10 to the worst pain imaginable¹⁶. Pain intensity will be assessed twice, immediately after injection, and approximately 15 minutes thereafter, by asking the subject one of the following questions, as appropriate:

- "How would you rate the pain you have felt during the treatment, if "0" is no pain at all, and "10" is the worst pain you can imagine?"
- "How would you rate the pain you have felt during recovery from the treatment, if "0" is no pain at all, and "10" is the worst pain you can imagine?"

Subject's response will be recorded in the Pain assessment form and the CRF. To avoid overreporting of pain, a non-leading question *"How do you feel?"* should be asked prior to pain assessment. Only spontaneously reported pain, or pain graded \geq 4 will be recorded as an AE.

6.4.8 Subject's satisfaction assessment

Each subject will be asked to grade their satisfaction with the treatment using one of the following categories: "Very unsatisfied", "Unsatisfied", "Neither unsatisfied nor satisfied", "Satisfied", or "Very satisfied".

The statement selected by the subject will be recorded in the Subject's satisfaction form and the CRF.

6.4.9 Outcome evaluation by the independent reviewer of photographs

An independent reviewer will evaluate the treatment outcome using the NLF-SRS scale and based on the photographs. Photographic reviewer, who will assess treatment effect based on photographs of the subjects, will be dislocated from the investigation sites and will not discuss any findings with the investigators or independent clinical evaluators during the trial and until the final database lock. Moreover, an evaluation of nasolabial folds severity by an independent blinded photographic reviewer using the 5-point NLF-SRS scale and based on photographs will take place at the end of the study.

6.4.10 Safety monitoring

The safety of the investigational device will be monitored throughout the investigation, from Day 0/visit 1 until the final visit (visit 5). AEs will be collected at each visit. In addition, the subjects will be instructed to immediately contact the investigator by phone in case of occurrence of any untoward event between the visits. The procedure for collection, recording and reporting of AEs is described in Section 14.

6.4.11 Prior and concomitant medication and non-drug therapies

Prior medication is defined as all medication taken within 10 days (whether continuing or not) prior to Day 0. Concomitant medication is defined as all medication taken from Day 0 (including medication taken immediately pre-injection and post-injection) until the Week 36 visit.

At each visit the subject must be asked about any new medication taken or changes in current medication, as well as, about any aesthetic procedure applied in the area treated with the investigational device.

All prior and concomitant medication and non-drug therapies will be recorded in the subject's medical record and the CRF.

Prohibited medication and aesthetic treatments

- Immune therapy, i.e., treatment with biologics designed to boost the body's natural defences (from Day 0 until the end of the clinical investigation)
- Anticoagulant, antiplatelet, or thrombolytic drugs (from 10 days pre- until 3 days post-injection)
- Facial surgery or implantation of dermal fillers other than the investigational device (from 12 months prior to Day 0 until the end of the clinical investigation)
- Absorbable and non-absorbable sutures (thread), laser therapy or dermabrasion (from 12 months prior to Day 0 until the end of the clinical investigation)
- Botulinum toxin treatment in the area treated with the investigational device (from 12 months prior to Day 0 until the end of the clinical investigation)
- Chemical peeling (from 3 months prior to Day 0 until the end of the clinical investigation)
- Skin needling or mesotherapy (from Day 0 until the end of the clinical investigation)

6.4.12 Factors that may compromise the outcome

There are no foreseeable factors that may significantly compromise the outcome. A substantial body weight change could possibly affect the results in individual subjects. Since this is a post-market investigation, designed to mimic a real-life situation, this random and relatively rare event that can either improve or deteriorate the outcome will not be controlled. It is possible that women will prevail in the study population, but this reflects common clinical practice.

6.5 Monitoring plan

The conduct of this clinical investigation will be monitored by the Sponsor's representative, who will appoint a Monitor of the investigation. The extent of monitoring and source data verification will be specified in the Monitoring plan.

Prior to initiation of the clinical investigation at any of the investigation sites, the Monitor will discuss the CIP and the CRF with the investigator and their staff. The site must not enroll any study participant before this initiation visit. During the investigation, further monitoring visits will be performed according to ISO 14155:2011, the applicable standard operating procedures, and local regulations. The CRF will be reviewed against source data for adherence to the CIP, as well as for completeness, accuracy and consistency of data. Additionally, the Monitor will check the progress of enrolment, and will ensure that the investigational device is stored, dispensed and accounted for according to the respective specifications. Key study personnel must be available to assist the Monitor during these visits. The Monitor will inform the investigator or their authorized designee of any CRF entry error, omission, or illegibility. The Monitor should ensure that appropriate corrections, additions, or deletions are made, dated, explained (if necessary), and initialed by the investigator or their authorized designees.

The investigator and their institution must permit the monitoring of the investigation, and provide the Monitor direct access to those portions of the subject's primary medical records, which directly concern this clinical investigation.

7 Statistical considerations

Planned statistical analyses are briefly summarized below. Data analyses will be described in detail in the Statistical analysis plan (SAP).

7.1 Sample size

Up to 60 subjects with moderate to severe nasolabial folds will be enrolled in order to obtain the 24-week performance and safety data from at least 40 of them. If less than 60 subjects will be recruited at the point when at least 40 subjects complete the Week 24 assessment, a decision to continue the recruitment up to 60 subjects in total will be made by the Sponsor. This sample size is arbitrarily selected and is considered appropriate for the post-market follow-up clinical investigation and sufficient to provide robust estimations on performance and safety parameters in the study population. With a sample size of 60, a two-sided 95% confidence interval for a single proportion using the large sample normal approximation will extend 0.076 from the observed proportion for an expected proportion of 0.900. Thus, a robust estimation of the success rate at week 24 can be derived..

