6.1.5 Replacement of subjects

Subjects withdrawn from the investigation or lost for follow-up will not be replaced.

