7.3 Missing data

Missing data will not be estimated and/or imputed in any way.

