Sample size calculation was performed by the sponsor. Up to 60 subjects with moderate to severe nasolabial folds will be enrolled in order to obtain the 24-week performance and safety data from at least 40 of them. If less than 60 subjects will be recruited at the point when at least 40 subjects complete the Week 24 assessment, a decision to continue the recruitment up to 60 subjects in total will be made by the sponsor. This sample size is arbitrarily selected and is considered appropriate for the post-market follow-up clinical investigation and sufficient to provide robust estimations on performance and safety parameters in the study population. With a sample size of 40 to 60, a two-sided 95% confidence interval for a single proportion using the large sample normal approximation will extend 0.076 to 0.093 from the observed proportion for an expected proportion of 0.900. Thus, a robust estimation of the success rate at week 24 can be derived.

Study and treatment duration

The duration of the clinical investigation will be 9 months for each participating subject. A single application of Princess® VOLUME Lidocaine, with optional Touch-up treatment after two weeks, if the desired level of correction has not been achieved with the initial application, is planned.

The total expected duration of the clinical investigation is about 13 months with an expected recruitment period of 3 to 4 months.

2 Performance and Safety Endpoints

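### Protocol 7.1 gives Week 24 precision for 60 subjects only, although its Week 24 target is at least 40, and the SAP plans no confidence interval for the responder proportion

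*Protocol*

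**What the plan says.** Protocol 7.1 caps enrolment at 60 and gives the purpose: subjects "will be enrolled in order to obtain the 24-week performance and safety data from at least 40 of them". It leaves the sponsor to decide whether to go on to 60: "If less than 60 subjects will be recruited at the point when at least 40 subjects complete the Week 24 assessment". It then gives one precision figure: "With a sample size of 60, a two-sided 95% confidence interval for a single proportion using the large sample normal approximation will extend 0.076". The success rate assumed for this figure is 0.900. From this it concludes: "Thus, a robust estimation of the success rate at week 24 can be derived".

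Two other sections bear on how many Week 24 values there will be. Protocol 6.1.5: "Subjects withdrawn from the investigation or lost for follow-up will not be replaced". Protocol 7.3: "Missing data will not be estimated and/or imputed in any way".

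The SAP, under Number of subjects, carries nearly the same paragraph but gives the precision for 40 to 60 subjects: the interval "will extend 0.076 to 0.093 from the observed proportion for an expected proportion of 0.900". SAP section 6, which lists deviations from the protocol, does not mention this difference.

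The proportion concerned is the second primary endpoint, a reduction of at least 1 point in NLF-SRS grade at Week 24 (Protocol 6.1.1, SAP 2.1). SAP 4.3.1 plans a 95% confidence interval for the mean change but only frequency tables for this proportion. Protocol 7.4.1 does the same.

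**The concern.** The conclusion about the Week 24 success rate rests on the best case. Sixty Week 24 values require all 60 subjects to be enrolled and every one of them to have a Week 24 grade, since dropouts are not replaced and gaps are not filled. The number the paragraph itself aims for is 40, and the precision at 40 does not appear in the protocol.

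Two related matters follow. First, the normal approximation is a poor choice for a proportion near 0.90 with samples of this size: at 40 subjects only 40 × 0.10 = 4 failures are expected. Second, the sample-size rationale relies on a confidence interval for the responder proportion, but the analysis plan never asks for one.

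The stake is modest. The sample size is described as arbitrarily selected and there is no hypothesis test (Protocol 5.2), so this sentence is the only quantitative support for the size. A reader of the protocol alone would expect tighter Week 24 precision than the stated target gives. A reader of the results would get a primary responder percentage with no measure of its uncertainty.

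**Working it through.** **Inputs.** Expected proportion p = 0.900, two-sided 95% confidence, normal approximation, n = 60 (Protocol 7.1); n = 40 to 60 (SAP, Number of subjects); Week 24 target of at least 40 (Protocol 7.1).

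**Step 1: reproduce the plan's figures.** Half-width = 1.960 × √(p(1 − p)/n).

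- n = 60: 1.960 × √(0.09/60) = 0.0759, the protocol's 0.076.
- n = 40: 1.960 × √(0.09/40) = 0.0930, the SAP's 0.093.
- n = 50, for reference: 0.0832.

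A continuity-corrected interval (0.0842) or a one-sided multiplier (0.0637) at n = 60 does not match, so the plain two-sided normal-approximation formula was used.

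**Step 2: size of the difference.** √(60/40) = 1.22, so the half-width is about 22% wider at 40 than at 60. In absolute terms this is 0.093 − 0.076 = 0.017. Around 0.90 the interval is about 0.824 to 0.976 at n = 60 and 0.807 to 0.993 at n = 40.

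**Step 3: does the normal-approximation interval cover 95%?** For each possible number of successes, form the interval and see whether it contains 0.90. Then add the binomial probabilities, at p = 0.90, of the counts for which it does.

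| n | Counts whose interval contains 0.90 | Exact coverage, normal approximation | Exact coverage, Wilson |
|---|---|---|---|
| 40 | 31 to 38 | 91.4% | 94.3% |
| 50 | 40 to 47 | 87.9% | 97.0% |
| 60 | 48 to 57 | 94.1% | 95.2% |

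At n = 40 the normal-approximation upper limit also exceeds 1 for 37, 38 or 39 successes.

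**Step 4: intervals suited to this setting, for an observed 90%.**

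| Successes/n | Wilson | Exact (Clopper-Pearson) |
|---|---|---|
| 36/40 | 0.769 to 0.960 | 0.763 to 0.972 |
| 54/60 | 0.799 to 0.953 | 0.795 to 0.962 |

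The Wilson half-widths are (0.960 − 0.769)/2 ≈ 0.095 and (0.953 − 0.799)/2 ≈ 0.077. These are within about 0.002 of the normal-approximation values. What changes is where the interval sits and how well it covers, with little effect on its width.

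**The case against.** The strongest reply is that nothing is miscalculated or hidden. The protocol sentence is openly conditional on 60, the minimum of 40 stands in the same paragraph, and section 7 says that it only summarises and leaves the detail to the SAP. The SAP, finalised before the first subject was enrolled, gives the figure at 40. All of this stands, and it rules out some stronger readings:

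- *The 0.076 is an arithmetic error.* It is not. It reproduces exactly for n = 60; the issue is which n it is quoted for.
- *The protocol and SAP contradict each other.* They do not. Both give 0.076 at 60, and the SAP adds the less favourable end.
- *Forty Week 24 values are assured.* They are not. Forty is a target, and without replacement no Week 24 number is guaranteed.
- *The trial will report an interval with about 91% coverage.* The documents do not support this. The normal-approximation interval is used for planning only, and no interval for the proportion is planned.

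It is also fair to say that 40 is the far end of the range. With 60 enrolled it needs a loss of 20/60 = 33%. If recruitment takes the expected 3 to 4 months, it closes before 40 subjects could reach Week 24, so the option to stop below 60 matters only if recruitment is slow. If losses were 10% to 20% (an assumption, since the documents give no dropout rate), n would be 54 to 48 and the half-width 0.080 to 0.085. Coverage at a single true proportion is also erratic from one n to the next, so the three values in the working show that coverage falls short of 95% but do not describe a smooth trend.

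These arguments keep the point small. They do not explain why the protocol omits the precision at its own target, and they do not supply the missing interval for a primary endpoint.

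**Conclusion.** The point holds as a minor one of incomplete reporting. The protocol's 0.076 is the best-case half-width; at the stated Week 24 target it is 0.093, and any n between 40 and 60 lies between the two. The SAP has the full range, so what the protocol needs is alignment.

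The more useful part concerns the analysis. The responder proportion is a primary endpoint and its precision is the stated rationale for the sample size, yet SAP 4.3.1 gives it no interval. If the normal-approximation interval from the planning text were simply carried over, its coverage at a true proportion of 0.90 would be 87.9% to 94.1% for the three sample sizes checked.

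The figures assume the plan's expected proportion of 0.90 and one binary outcome per subject. No test, threshold or decision rule depends on them.

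**What to change.** 1. In Protocol 7.1, state the precision for 40 to 60 subjects with Week 24 data, in line with the SAP's 0.076 to 0.093. Preferably give Wilson limits for an observed 90%: about 0.77 to 0.96 at 40 and 0.80 to 0.95 at 60. Describe 40 as the target minimum, not as an assured number.
2. In the SAP's Number of subjects paragraph, use the same interval method, so that planning and analysis agree.
3. In SAP 4.3.1, add a two-sided 95% Wilson (or exact) interval for the Week 24 responder proportion, next to the frequency table.

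The cost is a slightly less favourable stated figure and one extra table column. No additional subjects, visits or assessments are needed.
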